1.21. Risks and expected adverse events

1.21.1. Risk Determination

All study procedures involve no more than minimal risk to participants. Similar procedures have been used for many years without severe adverse effects. These include blood and nasal sampling; participants will be counselled as follows:

Blood draws: risks include discomfort as the needle goes through the skin and/or bruising. Infection, excess bleeding, clotting, or fainting are also possible, although unlikely.

Nasal lavage (washings), SAM strips (a soft strip placed up the nose for two minutes), and nasal curettage (scrape): may tickle, make their eyes water or be slightly uncomfortable. They should not be painful. The throat and oral swabs are not painful.

Four devices are to be used within the study. All will be connected to a mobile device, which will have dedicated applications for data collection. All data collection will be via Bluetooth, with other connection methods deactivated, to reduce the risk of data loss or breach.

Bittium Faros device: risks are similar to typical wearable devices, the only known physical risk related to wearing these types of sensors relates to skin irritation caused by the electrodes. The device is not intended to be used at the same time with high frequency (HF) surgical equipment or with defibrillator, of which neither situation should arise during the study. If such a situation arises, the device will be removed. Participants will be counselled about this specifically.

Lumee oxygen sensor insertion using the Lumee Pen: risks include possible local bruising, minor discomfort during skin injection, allergic reaction, redness, bleeding, infection, itching, irritation, fibrosis and discolouration of skin at insertion site. The sensor is not removed following the study but is invisible and rarely palpable, with no long-term risks having been identified in pre-clinical and clinical testing.

Lumee Patch reader: temporary skin irritation and temporary redness are possible where the patch is in contact with skin. Minor eye injury or irritation (comparable to looking directly into sunlight) may occur if the reader is not used properly and the light from the reader shone directly into the eyes. Participants will be counselled specifically to avoid this.

Lumee sensor removal: the sensor is not intended to be removed following the study but can be removed if the participant specifically requests it. Removal of the sensor is a minor surgical procedure and as such may cause scarring, pain, bleeding, infection, and allergic reactions to local anaesthetic. Participants will be counselled about these specific risks if they request sensor removal.

Biovotion Everion device: risks are similar to typical wearable devices; the only known physical risk related to wearing these types of sensors relates to skin irritation. The device will be removed once per day for around an hour for charging, allowing the skin to breathe and to permit washing and showering.

For the study protocol as a whole, there is no more than minimal risk for minor side-effects or adverse reactions aside from the expected adverse events related to influenza infection.

1.21.2. Potential adverse events related to influenza infection

We would expect subjects to experience typical symptoms of a common cold (including, but not limited to: fever, headache, malaise, rhinorrhoea, nasal congestion, sneezing, sore throat, and cough). These would not be deemed adverse events, unless in the opinion of the study doctor. However, fever greater than 38°C for more than three consecutive days or withdrawal from the study due to intolerable symptoms in more than two subjects will lead to a suspension of the study. The safety monitoring committee will be convened to determine any systematic cause for unexpectedly severe symptoms.

Any influenza-like illness resulting in

- **Sustained elevated heart rate >120bpm AND sustained low blood pressure SBP<100**
- **Sustained elevated respiratory rate >30/min AND sustained low blood oxygen SaO₂<94%**
- **Evidence of pneumonia on clinical examination**
- **New ECG abnormalities (compared to baseline)**

will lead to discussion with the Principal Investigator and possible referral for assessment in Accident and Emergency. Hospitalisation of any subject will lead to immediate suspension of the trial. The safety monitoring committee will be convened to assess the clinical evidence in order to determine whether the study may proceed.

1.21.3. Potential adverse effects of chest x-ray

Each volunteer who is eligible to enter into the study will have a single chest X-ray at baseline prior to inoculation, which is entirely for research purposes. The estimated dose will be 0.014mSv (table 11, HPA-CRCE-012 2010 dose review) which is approximately equivalent to 2.5 days natural background radiation and carries risk of inducing a cancer of approximately 1:1,400,000 based on risk factors for a healthy adult. This is classified as a trivial risk level (ICRP 62).

1.22. Reporting procedures

A Safety Monitoring Committee (SMC) will be established to advise the trial team on study progression in the event of a safety issue. The SMC will be informed of all unexpected AEs at least monthly during the clinical study period and convene during the study if there are any serious adverse events, protocol deviations, or other safety issues. The SMC will be appointed and meet once (in person or by teleconference) prior to commencement of the study. It will consist of at least three members independent of the study team experienced in clinical trials and experimental medicine, with at least one member familiar with human challenge studies and one member experienced in respiratory infections. If any pausing rules or other safety issues arise, they will be convened to assess the clinical data and make a judgment on whether the study can proceed. In addition, study conduct will be monitored by a non-medical study monitor and medical monitor appointed by Duke University.

All adverse events should be recorded in the clinical record form. Depending on the nature of the event the reporting procedures below should be followed. Any questions concerning adverse event reporting should be directed to the Chief Investigator in the first instance. In the event of an SAE, an SAE form should be completed and emailed to the Chief Investigator and the Sponsor within 24 hours of the event having been discovered by or notified to the study team. The safety monitoring committee, Duke medical monitor and co-investigator will also be informed within 24 hours and a meeting of the SMC convened as soon as possible.

All SAEs should be reported to the West London REC 2 Research Ethics Committee where in the opinion of the Chief Investigator, the event was:

- 'related', i.e. resulted from the administration of any of the research procedures AND
- 'unexpected', i.e. an event that is not listed in the protocol as an expected occurrence

Reports of related and unexpected SAEs should be submitted to ethics, the sponsor and the R&D office within 15 days of the Chief Investigator becoming aware of the event, using the NRES SAE form for non-IMP studies.

All non-compliance/unanticipated problems, adverse events, audits and investigation reports will be reported to DON HRPP and SSC Pacific.

The US Research Monitor (appointed by Duke University and approved by the Human Research Protection Office [HRPO] of the US Department of Defense) will be [name]. The US Research Monitor is responsible for overseeing the safety of the research subjects and, when unanticipated problems involving risks to subjects or others associated with the protocol, for reporting of findings to the Institutional Review Board (IRB) or a designated institutional official. The US Research Monitor may discuss the research protocol with the investigators and may recommend that the PI/Sponsor stop a research protocol in progress, remove individual human subjects from a research protocol, and take whatever steps are necessary to protect the safety and well-being of human subjects pending review by the IRB and/or SMC (see Monitoring SOP). Furthermore, they shall have the responsibility to promptly report their observations and findings to the ethics committee or other designated official and the HRPO.

1.22.1. Non serious AEs

All such events, whether expected or not, should be recorded. These will be discussed by the safety monitoring committee (see Section 12)

1.22.2. Serious AEs

An SAE form should be completed and faxed to the Chief Investigator and the Sponsor within 24 hours. The safety monitoring committee (see Section 12) will also be informed and a meeting convened as soon as possible.

All SAEs should be reported to the NRES London-Fulham Research Ethics Committee where in the opinion of the Chief Investigator, the event was:

- ‘related’, i.e. resulted from the administration of any of the research procedures; and
- ‘unexpected’, i.e. an event that is not listed in the protocol as an expected occurrence

Reports of related and unexpected SAEs should be submitted to ethics, the sponsor and the R&D office within 15 days of the Chief Investigator becoming aware of the event, using the NRES SAE form for non-IMP studies.

Contact details for reporting SAEs

[contact] for the attention of [name]

**Please send SAE forms to: Infectious Diseases & Immunity, Imperial College London,
[name]
[contact] (Mon to Fri 09.00 – 17.00)**

ASSESSMENT AND FOLLOW-UP

Study participants will be seen frequently during the study period, and at least daily during the confinement period following infection. They will be given details to contact the study doctor and research nurses at any time and will be offered daily telephone contact. In this way, participants will be assessed regularly by the investigating team and any adverse events detected rapidly; subjects meeting the criteria for a serious adverse event will be offered prompt treatment as appropriate.

Subjects will have completed the main study when they have had final convalescence investigations, expected to be 28 days after the initial inoculation with the influenza virus. Additionally, they will be invited to return for a further visit at 6 months for sampling to assess their longer-term immunity. The overall study will be completed when sufficient numbers of subjects have been recruited. The end of the study is defined as the last visit of the last participant.

When the study is completed they will not be routinely followed-up. Subjects will return to the care of their GP following completion of the study.

If a participant loses capacity during the study, then the participant would be withdrawn from the study. Identifiable data or tissue already collected with consent would be retained and used in the study. No further data or tissue would be collected or any other research procedures carried out on or in relation to the participant.

The study is a low-risk non-CTIMP, carried out by an experienced PI and study team. The study has appropriate risk assessments in place and will be checked through the PRB system at ICRF.

Local monitoring will be carried out by study staff to ensure that CRFs are being completed, with no key data missing. Duke University will appoint one of their in house monitors to check the data produced, paper CRFs will be uploaded to their eCRF system. The monitor will check consent forms and data logs.

STATISTICS AND DATA ANALYSIS

Sample size estimation: the goal of this study is a proof-of-concept demonstration that physiological measures can detect influenza infection in the pre-symptomatic phase. As such, it is not possible to carry out a formal power analysis to determine the sample size, since no preliminary data on the effect size in influenza infection using the sensors in this study are available. However, heart rate variability (HRV) parameters have been shown to enable detection of sepsis with 86% sensitivity and 100% specificity in a study of 17 subjects (14 positive and 3 negative for sepsis)⁵. Therefore, we aim for a similar target for numbers of symptomatically infected individuals (13-15), which is likely to be achieved with a sample size of 20 subjects based on the previously established attack rate of 75% using this challenge virus. Larger studies would be required in the future to generate generalizable detection statistics, but the 20-subject sample size proposed here should be sufficient for concept demonstration.

Quantitative assessments of symptom scores, lung function, virus load, leukocyte numbers and inflammatory markers will be compared within subjects to determine differences between baseline and during infection. Intra-subject differences will be analysed using ANOVA and 2-tailed paired Student's t-tests or Wilcoxon signed rank test as appropriate. Correlations between inflammatory cell, illness severity, viral load and leukocyte counts will be examined using Spearman's rank correlations to investigate possible causal relationships.

We aim to determine if the different sensors in the study can measure changes associated with influenza infection. For each sensor we will define and compute multiple metrics from the raw sensor output. Each of these metrics will be compared in the healthy versus sick states for each subject. We will consider a metric to be a potential predictor of illness in a single subject if there is a significant ($p < 0.05$) difference between the mean value in the sick and healthy state. Control comparisons will be made by computing the significance of differences between two different healthy periods (e.g. prior to infection and post recovery).

The potential predictors of illness from the within subject analysis will be compared across all subjects to determine if any sensor metrics provide generalizable indicators of illness. A metric will be considered a valid indicator if it is present in at least 85% of the within subject sick/healthy comparisons and less than 25% of the within subject control comparisons. This odds ratio is sufficient to achieve 80% power and a 5% error rate with a sample size of 13 subjects. Based on an established attack rate of 75% with this challenge virus, we estimate that will have 15 of our 20 subjects develop influenza. Therefore, the sample size of this study is sufficient to determine the feasibility of using the selected sensors to measure changes associated with influenza.

Data and all appropriate documentation will be stored for a minimum of 10 years after the completion of the study, including the follow-up period according to Imperial College London policy.

REGULATORY ISSUES

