1.2. Research Hypotheses

1. Novel wearable sensors (i.e, Bittium Faros, Biovation Everion, and Profusa Lumee) can detect physiologic changes that are associated with influenza infection and disease severity.
2. Physiologic patterns of heart rate, physical activity, ECG, respiratory rate and oxygen saturation from wearable sensors can act as biomarkers that enhance current diagnostic practice for early detection of influenza infection and disease prediction.

STUDY OBJECTIVES

1.3. Primary Objective:

- To test the hypothesis that measurements of heart rate, physical activity, ECG, respiratory rate and oxygen saturation can detect influenza infection and disease

1.4. Secondary Objective:

- To identify early signatures using sensor data that predict influenza disease and severity, potentially enabling earlier medical or public health interventions

1.5. Exploratory Objectives:

- To test the associations between physiologic sensor measurements and cognitive function using objective tests
- To test the associations between physiologic sensor measurements and biological and immune readouts

PARTICIPANT ENTRY

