Lumee reader			X	X	X	X	X	X	X	X	X	X	X	X	X	X	X	X	X	X	X	X	X		
Symptom diary			X	X	X	X	X	X	X	X	X	X	X	X	X	X	X	X	X	X	X	X	X	X	
Urine tests		X				X																			
Cognitive test: Visual Arrays test					X									X									X		
Cognitive test: Sustained Attention to Cue task						X									X									X	
Cognitive test: Ant-Saccade test							X								X								X		
Mind in the eyes questionnaire						X									X								X		
Social Support questionnaire							X																		

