1.19.4. Computerised Attention tests

Attention control tests assess the ability to concentrate on a task and distractibility¹⁶. We hypothesise that the onset of influenza infection leads to changes in ability to concentrate that occur before symptoms are noticeable. Three computerised tests will be administered. Following explanation of how the tests will be conducted, a laptop computer with tests pre-loaded will be given to the participant and how the tests are done will be explained to them. They will self-administer the test. Data will be labelled only the participant identification number only and stored on the laptop until the end of the study.

Visual Arrays test: Each trial begins with a reminder to subjects of how to record their responses. Afterward, subjects see a fixation cross displayed on the screen for 1000 ms, which they are asked to focus on, followed by the words “RED” or “BLUE” for 300 ms. This instructs participants to pay attention to only the red or the blue rectangles on the next screen. For example, “BLUE” tells participants that they will later be asked about the blue rectangles. Next, an array of blue and red rectangles is presented for 250 ms. It consists of either 5 or 7 rectangles per colour (10 and 14 total) scattered around the screen.

[figure not shown]

Figure 5: Visual Arrays test

After a delay of 900 ms, the array is presented again, this time with only the bars of the relevant colour. One of the rectangles is cued with a white dot. Subjects must indicate whether the indicated rectangle has changed orientations from the first presentation of the array. Cued rectangles change orientation on 50% of all trials. There are 48 trials of both the 10- and 14-item arrays, for a total of 96 trials. The dependent variable is a capacity score (k), one for each array size. The final dependent variable is the mean of these two k scores.

Administration of this task takes approximately five minutes and requires a standard computer mouse and QWERTY keyboard. The test will be administered three times during the study – at entry, at 3-4 days post exposure, and at pre-discharge.

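### The stated goal is pre-symptomatic detection, but no planned sensor comparison isolates pre-symptomatic time, so a metric that changes only during symptoms can be declared a valid indicator

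*Combined protocol and SAP*

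**What the plan says.** All references are to the combined protocol and SAP.

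- **Goal.** The sample-size paragraph of Statistics and Data Analysis states that "the goal of this study is a proof-of-concept demonstration that physiological measures can detect influenza infection in the pre-symptomatic phase".
- **Objectives.** The primary objective (1.3) is to test whether "measurements of heart rate, physical activity, ECG, respiratory rate and oxygen saturation can detect influenza infection and disease", with no restriction to the time before symptoms. The secondary objective (1.4) is "To identify early signatures using sensor data that predict influenza disease and severity".
- **Sensor analysis.** Several metrics are computed per sensor, and "Each of these metrics will be compared in the healthy versus sick states for each subject". A metric is a potential predictor in one person if the two state means differ at p < 0.05. In addition, "Control comparisons will be made by computing the significance of differences between two different healthy periods", with the periods before infection and after recovery as the example.
- **Success rule.** A metric is a valid indicator if it is significant in 85% or more of the sick/healthy comparisons and in fewer than 25% of the control comparisons. The section attaches 80% power, a 5% error rate and 13 subjects to these two rates, and expects 15 of 20 participants to develop influenza.
- **Attention tests.** Section 1.19.4 says "We hypothesise that the onset of influenza infection leads to changes in ability to concentrate that occur before symptoms are noticeable". The sessions are "at entry, at 3-4 days post exposure, and at pre-discharge".

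**The concern.** The goal and the secondary objective are about the time before symptoms. The decision rule is about being ill. If the rule is followed as written, a metric can be called a valid indicator because it moves at the height of illness, when the participant already knows that he or she is unwell. The rule would then be met without answering the question that the sample-size paragraph poses. The reverse can also happen: a change confined to the early hours could be diluted or missed.

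The documents use the early period as the main rationale. Section 1.1 argues for finding changes that precede symptoms and cites pilot data on sleep disturbance within 24 hours of exposure. If the early window is chosen only after many metrics have been examined, a positive finding will carry little weight.

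**Working it through.** **Step 1. Where does pre-symptomatic time go?** Sick and healthy have no dates, no symptom threshold and no virological criterion. Two readings are possible.

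| Reading of sick | Where infected, pre-symptomatic time falls | Consequence |
|---|---|---|
| Symptomatic | Left out, or counted as healthy | Not tested, or it contaminates the baseline |
| All infected time after inoculation | Averaged with symptomatic days | A change at peak illness can carry the mean; an early-only change is diluted |

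Under the first reading, take a metric significant in 100% of participants while symptomatic, in 0% before symptoms, and in 0% of control comparisons. It scores 100% against the 85% threshold and 0% against the 25% ceiling, so it passes. Under the second reading it can also pass, if the symptomatic days shift the mean enough. No onset time has to be assumed for this.

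**Step 2. Does another analysis cover it?** The within-subject tests of baseline against infection in the same section list symptom scores, lung function, virus load, leukocyte numbers and inflammatory markers. Sensor metrics are not on that list. No analysis is assigned to the secondary objective. The clinical cold definition (1.19.3) uses totals over six days and does not give an onset time.

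**Step 3. Reproduce the 13.** Inputs from Statistics and Data Analysis: p1 = 0.85, p2 = 0.25, 80% power, 5% error. Assumption: two-sided, with 1.96 and 0.8416 as the normal quantiles.

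n = [1.96·√(2·p̄(1−p̄)) + 0.8416·√(p1(1−p1) + p2(1−p2))]² / (p1−p2)², with p̄ = (p1+p2)/2

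- p̄ = 0.55; n = (1.379 + 0.472)² / 0.36 = 9.52
- Continuity correction: n′ = (n/4)·[1 + √(1 + 4/(n·|p1−p2|))]² = (9.52/4)·[1 + √(1 + 4/5.712)]² = 12.63, so **13**

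The plan's figure is reproduced. It belongs to the sick/healthy rate set against the control rate.

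**Step 4. Same method, pre-symptomatic rate.** The documents give no pre-symptomatic detection rate, so it is varied as an assumption, with the control rate held at 25%.

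| Assumed pre-symptomatic rate | n before correction | n after correction | Expected cases (0.75 × 20) |
|---|---|---|---|
| 85% | 9.52 | 13 | 15 |
| 75% | 14.46 | 19 | 15 |
| 65% | 23.07 | 28 | 15 |
| 55% | 40.66 | 48 | 15 |

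Without the correction, rounding up gives 10, 15, 24 and 41. At 75% the answer therefore depends on the correction: 15 is just met without it and 19 is not met with it. At 65% and below, 15 cases fall short either way. Both comparisons come from the same people, so a paired method would suit better. The unpaired formula is used here because it returns the plan's own number.

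**Step 5. Attention tests.** By the text of 1.19.4 there is a session at entry and the next is 3-4 days after exposure, so none is scheduled between entry and day 3.

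**The case against.** The strongest reply is that the primary objective has no pre-symptomatic restriction and that sick versus healthy answers it. **This stands.** The gap concerns the stated goal and the secondary objective.

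A second reply is that sick is undefined and could include pre-symptomatic infected time, since the example healthy periods are before infection and after recovery. This also stands as a reading, so one cannot say that those days enter no test. It does not rescue the plan, because averaging them with symptomatic days still does not test them separately.

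A third reply is that this is a proof-of-concept study that leaves detection statistics to larger ones. That excuses modest precision. It does not excuse a success rule that can be met without touching the concept.

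A reader might also infer more than the documents support:

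- **That no early data are collected.** Sensors are issued at day -7 (1.17.1) and worn through confinement, and the diary runs daily from day -7 to day 14 (1.19). The gap is in the prespecified analysis.
- **That sick versus healthy is the only sensor comparison.** There is a control comparison, and the rule needs both. It does not address early detection either.
- **That a known share of post-inoculation days goes untested.** No onset time is given, so any such share rests on an assumed one.
- **That the attention tests miss the pre-symptomatic period.** No such period is defined. Their timing bears only on the hypothesis in 1.19.4, because the stated goal is about physiological measures.
- **That Table 1 puts a baseline attention test after inoculation.** As extracted, the row "Cognitive test: Ant-Saccade test" starts in the day 0 pm column and the last attention sessions fall in the day 14 or 28 columns. The Social Support questionnaire, due at entry by 1.19.6, also falls at day 0 pm, so the columns may have shifted in extraction. No bias can be claimed from this.

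**Conclusion.** The point holds for the sensor analysis. The stated goal and the secondary objective have no comparison that isolates time before symptoms, and the 85%/25% rule can be met by a metric that changes only during symptoms. This needs correcting before the data are analysed, because the rule as written can yield a conclusion that does not address the goal.

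The claim of 80% power with 13 subjects is arithmetically reproducible for sick versus healthy and does not carry over. If the pre-symptomatic detection rate were 75%, the same method needs 19 subjects; at 65% it needs 28; about 15 cases are expected. These figures rest on an assumed detection rate, an unchanged 25% control rate, and the two-sided continuity-corrected formula that returns the plan's 13.

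It would be too strong to conclude that the trial cannot inform early detection or that its primary objective is untested. The attention-test timing is a separate and minor point.

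**What to change.** 1. **Define onset.** Use the daily diary with a prespecified threshold above the participant's own pre-inoculation baseline, set so that one trivial symptom does not trigger it. State how infected participants who never develop symptoms are handled, since their window has no natural end.
2. **Define three windows per participant:** pre-inoculation baseline, inoculation to onset, and symptomatic.
3. **Prespecify the test of the goal.** Compare pre-symptomatic with baseline, using the same control comparison and a success rule of its own. Keep sick versus healthy as a separate result for the primary objective.
4. **Limit the power statement.** Say that 80% power applies to sick versus healthy only, and give the range above for the pre-symptomatic test. The same section also says that a formal power analysis is not possible; reconcile the two statements.
5. **Attention tests (minor).** Drop the before-symptoms hypothesis in 1.19.4 or move the middle session earlier. Check the attention-test columns of Table 1 against the original document.

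Items 1 to 4 are analysis-plan wording and use data already scheduled. Moving a session would change the protocol schedule. The main cost is statistical: the window is short, so power is lower, and a null result there would be weak evidence against early detection.
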